3.3.2 Inclusion criteria

1. Of legal age (according to local legislation) at screening. No upper limit.
2. Signed and dated written informed consent in accordance with International Council on Harmonisation (ICH) Good Clinical Practice (GCP) and local legislation prior to admission to the trial.
3. Male or female patients. Women of childbearing potential (WOCBP)¹ and men able to father a child must be ready and able to use highly effective methods of birth control per ICH M3 (R2) that result in a low failure rate of less than 1% per year when used consistently and correctly, starting with the screening visit and through 6 months after the last dose of study treatment. A list of contraception methods meeting these criteria is provided in the patient information. The requirement of contraception does not apply to women of no childbearing potential and men not able to father a child, but they must have an evidence of such at screening.
4. Eastern Cooperative Oncology Group (ECOG) performance status: 0 to 1
5. Patients with a confirmed diagnosis of advanced, unresectable and/or metastatic solid tumours, who have failed standard treatment, or for whom no therapy of proven efficacy exists, or who are not amenable to standard therapies.
6. Presence of at least one measurable lesion according to RECIST 1.1.
7. Life expectancy of at least 12 weeks after the start of the treatment according to the Investigator's judgement
8. For Part B: Patients must have at least 1 tumour lesion amenable to biopsy, and must be willing to undergo a biopsy prior to first treatment and after 3 weeks while on therapy.
9. For Part B: Patients with following cancer types: bladder, colon, breast, NSCLC, ovarian, pancreatic, renal, esophagogastric, sarcoma, prostate, and melanoma.

¹ A woman is considered of childbearing potential (WOCBP), i.e. fertile, following menarche and until becoming post-menopausal unless permanently sterile.

Permanent sterilisation methods include hysterectomy, bilateral salpingectomy and bilateral oophorectomy.

Tubal ligation is NOT a method of permanent sterilisation.

A postmenopausal state is defined as no menses for 12 months without an alternative medical cause.

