 - Patients with an ejection fraction (EF) of either $<50\%$ or less than the lower limit of normal of the institutional standard will be excluded, whichever is lower. Only in cases where the Investigator (or the treating physician or both) suspects cardiac disease with negative effect on the EF, will the EF be measured during screening using an appropriate method according to local standards to confirm eligibility (e.g., echocardiogram [ECHO], multi-gated acquisition scan [MUGA]). A historic measurement of EF no older than 6 months prior to first administration of study drug can be accepted provided that there is clinical evidence that the EF value has not worsened since this measurement in the opinion of the Investigator or of the treating physician or both.
11. Inadequate organ function or bone marrow reserve as demonstrated by the following laboratory values:
 - Absolute neutrophil count (ANC) $<1.5 \times 10^9/L$ ($<1500/\text{mm}^3$)
 - Platelet count $<100 \times 10^9/L$ ($<100,000/\text{mm}^3$)
 - Haemoglobin $<9.0 \text{ g/dL}$

Proprietary confidential information © 2021 Boehringer Ingelheim International GmbH or one or more of its affiliated companies

- Alanine transaminase (ALT) >3 times the upper limit of normal (ULN) if no demonstrable liver lesion(s) (primary or metastases) or >5 times ULN in the presence of liver lesion(s)
- Aspartate aminotransferase (AST) >3 times the ULN if no demonstrable liver lesion(s) or >5 times ULN in the presence of liver lesion(s)
- Total bilirubin >1.5 times ULN, except for patients with Gilbert's syndrome who are excluded if total bilirubin >3.0 times ULN or direct bilirubin >1.5 times ULN
- Serum creatinine > 1.5 x ULN (measured by enzymatic assay, Isotope dilution mass spectroscopy [IDMS] standardised Jaffe assay, or non-IDMS Jaffe assay). If serum creatinine is > 1.5 x ULN, patient is eligible if concurrent estimated glomerular filtration rate (eGFR) is \geq 30 mL/min/1.73m² (measured or calculated by Chronic Kidney Disease Epidemiology [CKD-EPI] formula)

12. Human immunodeficiency virus (HIV) infection. Test results obtained in routine diagnostics are acceptable if done within 6 months before the informed consent date.

13. Any of the following laboratory evidence of hepatitis virus infection.

- Positive results of hepatitis B surface (HBs) antigen
- Presence of hepatitis B core (HBc) antibody together with hepatitis virus B (HBV) Deoxyribonucleic acid (DNA)

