In case less than 50% of a BI 754091 dose was administered due to CRS, a dose of 50% of the intended dose may be administered on the day when BI 891065 is re-started to ensure the patient receives an adequate dose of BI 754091. Please see section [3.3.4.1](#) regarding replacement of patients.
- In case of Grade 2 CRS, patients should be under close surveillance during the first 2 re-exposure administrations of BI 891065 and (if the CRS occurred during the or shortly after the infusion of BI 754091) during the first re-exposure administration of BI 754091 to ensure appropriate surveillance.

In the case of Grade 3 or 4 CRS, the study treatment should be permanently discontinued (section [4.1.6](#)).

Immune-related adverse event (irAE) (Part B only)

Immune-related AEs are AEs associated with immunotherapy treatments that appear to be associated with the immune therapy's mechanism of action. These adverse reactions, which can be severe, may involve the gastrointestinal, skin, liver, endocrine, respiratory, renal, or other organ systems. The Sponsor has defined a list of potential irAEs which need to be reported as AESI in section [10.1](#). If an Investigator determines another event (not on the list) should be a potential irAE, the Investigator may also report that event as an AESI.

Recommendations for the management of irAEs are presented in section [10.2](#).

Hepatic injury and potential drug-induced liver injury (DILI)

A potential hepatic injury is defined by the following alterations of hepatic laboratory parameters in patients with normal aminotransferase levels at baseline:

- an elevation of AST (Aspartate Aminotransferase) and/or ALT (Alanine Aminotransferase) ≥ 3 fold ULN combined with an elevation of total bilirubin ≥ 2 fold ULN measured in the same blood draw sample, or
- aminotransferase (ALT, and/or AST) elevations ≥ 10 fold ULN.

[figure not shown]
A potential hepatic injury is defined by the following alterations of hepatic laboratory parameters in patients with abnormal aminotransferase levels of $>$ ULN and ≤ 3 fold ULN at baseline:

- an elevation of AST and/or ALT ≥ 3 fold the baseline value combined with an elevation of bilirubin ≥ 2 fold the baseline value measured in the same blood draw sample, or
- aminotransferase (ALT, and/or AST) elevations ≥ 5 fold the baseline value.

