A potential hepatic injury is defined by the following alterations of hepatic laboratory parameters in patients with abnormal aminotransferase levels of >3 fold and ≤ 5 fold ULN at baseline (patients with liver metastases only):

- an elevation of AST and/or ALT ≥ 2 fold the baseline value combined with an elevation of bilirubin ≥ 2 fold the baseline value measured in the same blood draw sample, or
- aminotransferase (ALT, and/or AST) elevations ≥ 3 fold the baseline value.

These lab findings constitute a hepatic injury alert and the patients showing these lab abnormalities need to be reported according to Figure 5.2.6.1.4: 1, and be followed up according to the “potential DILI checklist” provided in the eDC system.

* Such as PD, viral hepatitis, and etc.

** Report as AESI even if PD is determined (PD exemption does not apply for Potential DILI cases)

*** Mark on DILI checklist that hepatic injury is due to a non-DILI etiology, such as PD, and submit DILI checklist & supporting source documents with SAE form

Figure 5.2.6.1.4: 1 Processing potential DILI cases

In case of clinical symptoms of hepatic injury (icterus, unexplained encephalopathy, unexplained coagulopathy, right upper quadrant abdominal pain, etc.) without lab results (ALT, AST, total bilirubin) available, the investigator should make sure these parameters are analysed, if necessary in an unscheduled blood test. Should the results meet the criteria of hepatic injury alert, the procedures described in the potential DILI checklist should be followed

The observation of the critical importance of altered liver function has been referred to informally as Hy's Law, and is described in the FDA's guidance on drug induced liver injury. Hy's Law cases have the following 3 components:

- The drug causes hepatocellular injury, generally shown by a higher incidence of 3-fold or greater elevations above the ULN of ALT or AST
- Among trial subjects showing such aminotransferase elevations, often with elevations much greater than 3 times ULN, one or more also show elevation of serum total bilirubin to >2 times ULN, without initial findings of cholestasis (elevated serum ALP)
- No other reason can be found to explain the combination of increased aminotransferase and total bilirubin, such as viral hepatitis A, B, or C; pre-existing or acute liver disease; or another drug capable of causing the observed injury.

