7.8.1 Adverse Events

The analyses of AEs will be descriptive in nature. All analyses will be based on the number of patients with AEs (not on the number of AEs). The analysis will be based on BI standards (6). AEs will be coded using the most recent version of MedDRA. According to the BI standards multiple overlapping or adjacent recordings (AE occurrences) of the same AE are collapsed into one AE event if all AE attributes are identical (lower level term, severity, action taken, therapy required, seriousness, reason for seriousness, relationship, outcome, AE of special interest (AESI) flag).

The analyses of AEs will be based on the concept of treatment-emergent AEs, where a treatment-emergent AE has an onset in the analysing treatment period. The AE analysis will be based on the on-treatment period which starts with the date of the first administration of study medication and ends 30 days after the last administration of study medication. AEs with an onset date in the screening period (time between informed consent date and date of the first administration of study medication) or follow-up period (time after the on-treatment period) will be tabulated and listed separately.

Sorting order: In AE tables, system organ classes (SOCs) will be sorted alphabetically and preferred terms (PTs, within SOCs) will be sorted by descending frequency.

Listings of AEs will be displayed by patient. The actual planned dose of BI 891065 will be derived and included in the listings. AEs will be reported with start day and end day as calculated from the first day of treatment with study medication. For listings displaying AEs during the screening or follow-up period, the start and stop day are calculated from the start of the respective analysis period.

The incidence of AEs overall, related AEs and serious AEs (SAEs) will be reported by severity according to common terminology criteria for adverse events (CTCAE) grades. Drug-related serious AEs will also be tabulated. Protocol-specified AESI will be analysed based on data reported in the eCRF.

AEs leading to death during the on-treatment period will be tabulated by SOC and PT. Reported fatal AEs during the follow-up period will be listed.

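### Patients with a primary liver lesion, no liver metastases and baseline ALT/AST above 3 to 5 times ULN are eligible for Part A but meet none of the hepatic-injury definitions

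*Protocol*

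**What the plan says.** Protocol 3.3.3, criterion 11, excludes a patient for ALT above 3 times ULN "if no demonstrable liver lesion(s) (primary or metastases) or >5 times ULN in the presence of liver lesion(s"). The AST bullet has the same split: "Aspartate aminotransferase (AST) >3 times the ULN if no demonstrable liver lesion(s) or >5 times ULN in the presence of liver lesion(s"). A liver lesion of either kind therefore raises the entry ceiling from 3 to 5 times ULN.

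Protocol 3.3.2 admits to Part A "Patients with a confirmed diagnosis of advanced, unresectable and/or metastatic solid tumours", and nothing in 3.3.3 rules out primary liver cancer. Part B has a closed list of tumour types that does not include it.

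Protocol 5.2.6.1.4 defines potential hepatic injury by baseline aminotransferases. The first definition applies "in patients with normal aminotransferase levels at baseline". The second applies above ULN and up to 3 times ULN. The third applies above 3 and up to 5 times "ULN at baseline (patients with liver metastases only"). There is no further band and no default rule. Meeting a definition is a hepatic injury alert, with its own reporting route and follow-up by the DILI checklist. Section 5.2.6.2.4 adds that the exemption of progressive disease from AE/SAE reporting does not apply to laboratory values that meet the definition.

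On analysis, SAP 7.8.1 states: "Protocol-specified AESI will be analysed based on data reported in the eCRF".

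**The concern.** The eligibility rule and the alert rule describe different populations at the same baseline level. Patients who enter with raised enzymes because of a primary liver lesion are ones in whom a further rise is easily put down to the tumour. The alert exists partly to stop that attribution from ending the enquiry, since it requires reporting and a checklist even when progression is the suspected cause. Without a definition, the safeguard has nothing to act on.

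The liver matters in this programme. Protocol 1.4.2 lists DILI as a risk and relies on timely detection, evaluation and follow-up to mitigate it. Section 1.2.3 reports raised bilirubin in 7 of 25 monotherapy patients in the first-in-human trial, apparently dose-dependent and still unexplained.

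**Working it through.** The plan gives no figure to reproduce. The check sets each baseline band and liver-lesion status against criterion 11 and the three definitions.

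| Baseline ALT/AST | No liver lesion | Liver metastases | Primary lesion, no metastases |
|---|---|---|---|
| Normal | eligible, covered | eligible, covered | eligible, covered |
| >ULN to 3x ULN | eligible, covered | eligible, covered | eligible, covered |
| >3x to 5x ULN | excluded | eligible, covered | **eligible, not covered** |
| >5x ULN | excluded | excluded | excluded |

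The first three rows have 3 × 3 = 9 cells. One is excluded, which leaves 8 eligible; 7 are covered and 1 is not.

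An illustration takes baseline ALT 4 and bilirubin 0.8 (both in multiples of ULN). Under the third definition the thresholds are:

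- combined: ALT at least 2 × 4 = 8 with bilirubin at least 2 × 0.8 = 1.6 in the same sample;
- isolated: ALT at least 3 × 4 = 12.

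**ALT rises to 13 alone.** 13 ≥ 12, so this is an alert with metastases. With a primary lesion only, no definition applies.

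**ALT rises to 9 with bilirubin 2.5.** 9 ≥ 8 and 2.5 ≥ 1.6, so this is an alert with metastases, and again no definition applies with a primary lesion only. However, 9 > 3 and 2.5 > 2, so it meets the combined DLT criterion in protocol 4.1.7 if there are no initial signs of cholestasis and the event is not unequivocally due to the malignancy or an extraneous cause. DLTs are AESIs under 5.2.6.1.4.

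Other rules that might fill the gap:

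- *DLT criteria (4.1.7).* They apply whatever the lesion type, but use fixed ULN multiples or toxicity grades. With this baseline, a bilirubin from 1.6 up to and including 2 would complete the third definition but not the combined DLT criterion. The grade-based criteria might catch some isolated rises; the documents do not reproduce the grade limits, so this cannot be settled here. The checklist is tied to the alert, not to DLTs in general.
- *Symptom-prompted testing (5.2.6.1.4).* It leads to the checklist only if the alert criteria are met, so it has the same gap.
- *SAP 7.8.2.* Potential Hy's law cases (ALT or AST above 3 times ULN with bilirubin at least 2 times ULN) are displayed for the whole treated set, and shift tables use multiples of the upper limit for ALT, AST and bilirubin. These include the uncovered patients, but they are retrospective. A baseline above 3 times ULN already meets the aminotransferase half of the Hy's law rule.

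**The case against.** The strongest case is that little escapes in practice. A combined rise like the second illustration is a DLT, is due to the sponsor within 24 hours and is an AESI. An isolated rise judged clinically relevant is still recorded as an AE. The SAP's explicit liver analyses have no restriction by baseline or metastasis. MTD estimation uses the DLT criteria, not these definitions. The reporting figure is not visible in the public text and the checklist sits in the data-capture system, so the implementation may be broader than the wording. By protocol version 5 one patient remained on treatment, and laboratory results were no longer collected in the eCRF.

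Most of this stands, and it limits the consequence. It does not remove the gap. A DLT can be set aside as unequivocally due to malignancy, and the override of the progression exemption works only for values that meet a hepatic-injury definition.

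The parenthesis might also be a mere remark that only patients with metastases can have such baselines. Criterion 11 contradicts that too, so the sections need reconciling on either reading.

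A reader might infer that all liver injury in these patients goes unreported, or that the SAP's liver analyses leave them out. The documents support neither: the DLT route and the whole-set tabulations remain. What may be missing is the hepatic-injury label in the AESI data, which come from what sites report.

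**Conclusion.** The inconsistency holds on the protocol's own text. One eligible category in Part A has no hepatic-injury definition, and so no alert, no checklist and no override of the progression exemption. The backstop is partial: it captures combined aminotransferase and bilirubin rises that pass the ULN-based thresholds and, for the DLT route, are not attributed to malignancy or cholestasis. It does not supply the alert or checklist for isolated aminotransferase rises.

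The number of patients cannot be estimated from the documents. An affected patient needs a primary liver lesion, no liver metastases and a raised baseline within a narrow band, and must also pass the bilirubin and hepatitis B and C criteria. About 12 patients were planned for Part A, so the number may well be zero. Part B is not affected: its tumour list omits primary liver cancer, and SAP section 3 records that it was cancelled.

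The conclusion assumes that the restriction in 5.2.6.1.4 is applied as written and that the figure and checklist do not widen it. The MTD is not in question. The point is worth correcting because it concerns safety reporting and costs almost nothing.

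**What to change.** Reconcile protocol 3.3.3 (criterion 11) with 5.2.6.1.4 so that eligibility and the hepatic-injury definitions refer to the same liver-lesion population and every eligible baseline category has an alert definition. Which section carries the intended population, and which thresholds apply, is for the sponsor's clinical team to decide. Bring the reporting figure, the checklist and any edit check into line with the outcome.

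Separately, check the baseline ALT/AST and liver-lesion records of all treated Part A patients. If any fell in the uncovered category, review their on-treatment liver values and say in the trial report how they were handled in the hepatic-injury AESI data. If none did, one sentence to that effect closes the point.

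The cost is a change of wording and one pass through data already collected. No new assessments are needed.

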5.2.6.1.5 Intensity (severity) of AEs

The intensity (severity) of adverse events should be classified and recorded in the CRF according to the Common Terminology Criteria for Adverse Events (CTCAE) version 5 ([R18-1357](#)).

5.2.6.1.6 Causal relationship of AEs

Medical judgement should be used to determine whether there is a reasonable possibility of a causal relationship between the adverse event and the given study treatment, considering all relevant factors, including pattern of reaction, temporal relationship, de-challenge or re-challenge, confounding factors such as concomitant medication, concomitant diseases and relevant history.

Arguments that may suggest that there is a reasonable possibility of a causal relationship could be:

- The event is consistent with the known pharmacology of the drug.
- The event is known to be caused by or attributed to the drug class.
- A plausible time to onset of the event relative to the time of drug exposure.
- Evidence that the event is reproducible when the drug is re-introduced.
- No medically sound alternative aetiologies that could explain the event (e.g. pre-existing or concomitant diseases, or co-medications).
- The event is typically drug-related and infrequent in the general population not exposed to drugs (e.g. Stevens-Johnson syndrome).
- An indication of dose-response (i.e. greater effect size if the dose is increased, smaller effect size if dose is reduced).

Arguments that may suggest that there is no reasonable possibility of a causal relationship could be:

- No plausible time to onset of the event relative to the time of drug exposure is evident (e.g. pre-treatment cases, diagnosis of cancer or chronic disease within days / weeks of drug administration; an allergic reaction weeks after discontinuation of the drug concerned).
- Continuation of the event despite the withdrawal of the medication, taking into account the pharmacological properties of the compound (e.g. after 5 half-lives). Of note, this criterion may not be applicable to events whose time course is prolonged despite removing the original trigger.
- Additional arguments amongst those stated before, like alternative explanation (e.g. situations where other drugs or underlying diseases appear to provide a more likely explanation for the observed event than the drug concerned).
- Disappearance of the event even though the trial drug treatment continues or remains unchanged.

5.2.6.2 Adverse event collection and reporting

5.2.6.2.1 AE Collection

The investigator shall maintain and keep detailed records of all AEs in the patient files.

The following must be collected and documented on the appropriate CRF(s) by the investigator:

- From signing the informed consent onwards until the 30-day follow-up-visit:
all AEs (non-serious and serious) and all AESIs.
- After the 30-day follow-up-visit until the individual patient's end of trial:
all related SAEs and all related AESIs.
- After the individual patient's end of the trial:
the investigator does not need to actively monitor the patient for new AEs but should report any new occurrence of cancer of new histology and trial treatment related SAEs and trial treatment related AESIs of which the investigator may become aware of by any means of communication, e.g. phone call. Those AEs should be reported on the BI SAE form (see section [5.2.6.2.2](#)), but not on the CRF.

The rules for Adverse Event Reporting exemptions still apply, please see section [5.2.6.2.4](#).

5.2.6.2.2 AE reporting to the sponsor and timelines

The investigator must report SAEs, AESIs, and non-serious AEs which are relevant for the reported SAE or AESI, on the BI SAE form via fax immediately (within 24 hours) to the sponsor's unique entry point (country specific contact details will be provided in the ISF). The same timeline applies if follow-up information becomes available. In specific occasions, the investigator could inform the sponsor upfront via telephone. This does not replace the requirement to complete and fax the BI SAE form.

With receipt of any further information to these events, a follow-up SAE form has to be provided. For follow-up information the same rules and timeline apply as for initial information. All (S)AEs, including those persisting after individual patient's end of trial must be followed up until they have resolved, have been assessed as "chronic" or "stable", or no further information can be obtained.

